Our overall goal is to develop and pilot a couple-therapy approach to Prolonged Exposure that integrates loved ones into every session of PE. We will combine techniques from Integrative Behavioral Couples Therapy and a brief, three-session approach to involving family in PE (Partner Enhanced Prolonged Exposure). We anticipate this intervention will teach couples to embrace a lifestyle that supports confronting trauma-related distress, so the veteran can achieve optimal functional recovery, while improving both social and family functioning. We will complete stages 1A and 1B of the Stage Model of Treatment Development.²⁵ This includes the following aims:

Aim 1: Expand our treatment outline using content experts and feedback from key **stakeholders** (veterans, loved ones, providers, and VA mental health leadership).

Aim 2: Conduct a pilot **open trial** to assess (a) the acceptability of treatment components, structure, and materials, (b) the feasibility of the intervention (retention and intervention fidelity), and (c) the study approach (screening, recruitment, and assessment process).

Aim 3: Explore the preliminary effects of the intervention on select outcomes including overall functioning, mental health functioning, social functioning, family functioning, and potential mechanisms (social control, subjective norms, and the degree to which veterans rely on their partners for support).

Impact: PTSD treatments (including PE and CPT) have been criticized for a narrow focus on symptom gains over goals that may be more meaningful to veterans, such as greater quality of life, interpersonal connections, and social functioning.^{26,27} Our proposal aims to expand the explicit targets of PE to these patient-centered outcomes. If our approach to a couple-based exposure therapy demonstrates promise, this proposal could provide the first step in a series of studies that **feed the evolution of one-on-one symptom-focused psychotherapies into family-based interventions designed to lift the whole household**. Our approaches could inform adaptations to interventions for a myriad of problems including suicide prevention, TBI rehabilitation, and pain management, contributing to a broader evolution towards evidence-based, family-inclusive care focused on outcomes with meaning to veterans.

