Veterans will also complete a posttreatment structured clinical interview for PTSD symptoms.⁵² Veterans and LOs will also complete 90-minute semi-structured qualitative exit interviews. All interviews will be conducted in person or by phone, based on the interviewee's preference, and will be audio-recorded. Qualitative exit interviews (Appendix 2) will assess (1) attitudes about intervention components, structure (e.g., level of therapist contact), and materials (e.g., handouts), (2) acceptability and efficacy of COACH, including suggestions for intervention improvement, (3) engagement with COACH, including retention and barriers/facilitators to engaging with the program, (4) perceptions of the impact of the program on the intervention targets (e.g., functioning, social control, subjective norms, and LO reliance) and exploration of unexpected domains impacted by the program, and (5) the completeness and time burden of the survey battery. We will also extract the following administrative data: (1) the number of sessions attended (from electronic medical record; retention), (2) the number of participants screened each month (screening), and (3) the number of eligible Veterans and LOs who declined participation (recruitment), and therapists ratings of homework compliance using two

5.6A. Risk to Subjects

A.1. Human Subjects Involvement and Characteristics

We aim to enroll 12 Veterans with PTSD at the Minneapolis VA and their loved ones. Veterans must (1) meet full criteria for PTSD on the CAPS⁵² and (2) have been in an intimate relationship for the last six months. Both members of the couple must be (3) willing to participate together in therapy, and (4) deny any episodes of

items adapted from the Patient Exposure and Response Prevention Adherence Scale (PEAS) for Obsessive Compulsive Disorder (also a cognitive-behavioral exposure therapy).⁶²

Table A. Data Sources					
Reporter	Baseline	During Treatment	Posttreatment	3-month follow-up	
Veteran	Structured Interview	Surveys assessing symptoms, weekly questions in preparation for therapy sessions for therapists, and treatment mechanisms	Structured Interview	Online measures	
	Online survey measures		Online survey measures		
			Qualitative Interview		
LO	Online survey measures	Surveys assessing symptoms, weekly questions in preparation for therapy sessions for therapists, and treatment mechanisms	Online survey measures Qualitative Interview	Online measures	

A.3. Potential Risks

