If a participant requests to have an informed consent meeting face-to-face with a study staff member, this will be permitted. Some participants may prefer to coincide other appointments at the VA with an in-person consent meeting with our study staff. Participants meeting in-person for informed consent will also be required to sign an official informed consent form, and a HIPAA authorization form.

Informed consent will be obtained before obtaining any Baseline self-reports or Baseline clinical interviews. As these Baseline procedures are also necessary for establishing final eligibility (SCID-5-CT and CAPS-5; IC: PCL-5, PHQ-9, AUDIT, DAST), Veterans will be notified that the baseline procedures are necessary for establishing final eligibility and they may be deemed ineligible for the study after these procedures. They will receive notification of their edibility and contacted by staff to schedule their first therapy appointment. Individuals deemed ineligible will be told by telephone and Veterans referred back to their referring providers.

When Veterans are deemed ineligible by a study assessor after completion of the Structured Clinical Interview (i.e., positive screens for psychosis, substance use, suicidality, homicidally, etc.), study staff will communicate the assessment results of these ineligible subjects back to the treatment team (non-study clinical staff) for purposes of patient treatment planning and continuity of care. Conveying a patient's assessment results to the treatment team allows patients to be referred to appropriate treatment in a timely manner, while also eliminating any inconvenient and redundant reassessments. This will be proposed to participants during informed consent, and patients will have the ability to decline this request

5.8B. LO Informed Consent

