For safety and risk implications, we will require Veteran and SP participants to retake the baseline survey and preclinical assessment if the therapy start date would occur 2 months after their baseline data was collected. Time gaps between baseline data and therapy start dates can occur for various reasons, including scheduling issues, provider availability, patient travel arrangements, etc. It is important that patient baseline data is as close to therapy start dates as possible, as clinical data can change over several weeks. For example, in the gap between assessment and therapy start, patients could have a serious substance use relapse or a suicide attempt that would then make it clinically inappropriate for them to begin a trauma-focused therapy, prior to addressing their more pressing concerns around establishing their safety or sobriety. Additionally, we expect many of the constructs we assess to naturally change with time (e.g., family functioning, relationship satisfaction). So, baseline assessments that are more than 2 months old at the time of therapy start may no longer truly represent the patient, support person, or family functioning at the beginning of treatment, confounding study results.

Subjects will be informed of this requirement during the informed consent process and on the information packet or informed consent form. Participants would get paid again for retaking these assessments (\$50 for the baseline survey; \$60 for the preclinical interview).

5.8D. Incentives.

Participants will receive \$40 for participating in Baseline surveys, \$50 for baseline diagnostic interviews (Veterans only), \$60 for posttreatment surveys, \$60 for posttreatment diagnostic interviews (Veterans only), and \$60 for one-time qualitative exit interviews. Both veterans and intimate partners will complete monthly surveys for outcomes and treatment mechanisms. They will receive \$25 for each of these surveys. Additionally, participants receive \$70 for completing a 3-month follow-up survey. A possible total of \$415 for veterans and \$305 for loved ones.

Participants will receive payment by direct deposit or debit card after completion of their baseline assessment and interview, post treatment assessment and interview, and exit interview.

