fidelity, screening, and treatment retention will be generated. We will calculate rates of survey non-response and item missingness for assessment feasibility. To preliminarily evaluate outcomes, we will calculate and graphically display the direction and magnitude of change from baseline to follow-up for outcomes outlined in Table 1. We will also calculate the percentage of participants who improved, worsened, and experienced no change for each of these measures. We will calculate descriptive statistics and pre-to-post treatment effect sizes. Lastly, we will triangulate our quantitative data with qualitative themes through matrices with exemplary quotations. Themes that emerge from the interviews will be stratified by participants' scores on relevant quantitative scales (e.g., participants' acceptability themes stratified by their Credibility-Expectancy and Satisfaction scores; feasibility themes stratified by number of sessions attended).

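### Symptom change is measured from a baseline that also selects veterans and may be about two months old at session 1, and Section 7.2 does not separate change before session 1 from change during treatment

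*Combined protocol and SAP*

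**What the plan says.** Section 7.2 describes the outcome analysis in three steps. First, "we will calculate and graphically display the direction and magnitude of change from baseline to follow-up for outcomes outlined in Table 1". Second, "We will also calculate the percentage of participants who improved, worsened, and experienced no change for each of these measures". Third, "We will calculate descriptive statistics and pre-to-post treatment effect sizes". No second pretreatment reference is named, and no analysis of the surveys collected during treatment is described.

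Section 5.8A explains that veterans may be found ineligible after baseline: "As these Baseline procedures are also necessary for establishing final eligibility". The list that follows includes the CAPS-5, PCL-5 and PHQ-9. Table 1 in Section 6.1 lists the same three as mental health outcomes.

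Section 5.8C requires the baseline to be repeated when therapy would start two months after it. Part of the reason given is that "we expect many of the constructs we assess to naturally change with time", and the section says that an older baseline would confound the results. It does not say which baseline is analysed after a retake.

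Table A in Section 5.6A lists, under the during-treatment column, "Surveys assessing symptoms, weekly questions in preparation for therapy sessions for therapists, and treatment mechanisms". The symptom instrument is not named and the symptom surveys have no stated frequency.

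Section 5.4 accepts that there is no comparator and names the pre-post design as a limitation, but discusses that design only in terms of length of follow-up. Regression to the mean is not mentioned.

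**The concern.** When a noisy score helps to decide who enters, those who enter have, on average, scored above their own usual level. Their next score tends to be lower without any treatment. If the same score is also the pretreatment value of the effect size, this fall appears as improvement.

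The wait between baseline and session 1 adds a second untreated component. Section 5.8C recognises it and caps it at about two months, but Section 7.2 does nothing with what remains under the cap.

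With a single arm, the pretreatment reference is the only point at which change before therapy can be told apart from change during it. The results are meant to support an application for a randomised trial (Section 5.1), so a directional error in the symptom effect size would carry forward. The improved/worsened/unchanged percentages are also exposed, because no threshold for change is given.

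**Working it through.** The plan states no effect size, SD or power figure, so there is nothing of its own to reproduce.

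**Inputs from the documents.** 12 veterans (Section 5.1; Section 5.3A says ten); 13-15 weekly sessions typically (Section 5.2A); posttreatment survey within four weeks of the last session (Section 6.1); baseline up to two months old (Section 5.8C).

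**Assumptions not in the documents.** Scores are bivariate normal; selection acts like a cut on the score, although the stated rule is a diagnosis; 50-90% of assessed veterans pass; retest correlation r is 0.7-0.9.

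**Regression to the mean with no treatment effect.** With pass rate p and cut c = Φ⁻¹(1 − p), the selected mean lies λ = φ(c)/p above the unselected mean. The expected fall is (1 − r)λ in unselected SD. The selected-sample SD is √(1 + cλ − λ²).

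Central case, p = 0.65 and r = 0.8:
- c = −0.385, λ = 0.370/0.65 = 0.570
- fall = 0.2 × 0.570 = 0.114 unselected SD
- selected SD = √(1 − 0.219 − 0.325) = 0.675
- fall = 0.114/0.675 = 0.17 selected-sample SD

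The full grid, in selected-sample SD (formula confirmed by simulation, 2,000,000 draws per cell):

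| Pass rate | r = 0.7 | r = 0.8 | r = 0.9 |
|---|---|---|---|
| 50% | 0.40 | 0.27 | 0.13 |
| 65% | 0.25 | 0.17 | 0.08 |
| 80% | 0.14 | 0.09 | 0.05 |
| 90% | 0.07 | 0.05 | 0.02 |

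In the central case 57% of veterans would improve by some amount with no effect, against 50% by chance (range 52-63%).

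These figures apply to a score on which selection acts directly. For another measure Z, standardised, selected through X, the fall is λ[corr(X₁, Z₁) − corr(X₁, Z₂)]. It is smaller when less of the momentary error is shared.

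**Precision.** The 95% half-width for a mean paired change is t(0.975, n − 1)/√n SDs of change: 2.201/√12 = 0.635 at n = 12. In the central case the SD of change is √((1 − r)² × 0.675² + 1 − r²) = √(0.018 + 0.360) = 0.615 unselected SD. The half-width is therefore 0.635 × 0.615/0.675 = 0.58 selected-sample SD, and 0.58/0.17 = 3.4 times the central bias.

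**Length of the wait.** Two months = 2 × 365.25/12/7 = 8.7 weeks. Counting one week per session, baseline to posttreatment runs from 8.7 + 13 + 0 = 21.7 to 8.7 + 15 + 4 = 27.7 weeks. At its ceiling the wait fills 8.7/27.7 = 31% to 8.7/21.7 = 40% of that window. A shorter course, which Section 5.2A permits, would raise the share.

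**What a session-1 score would remove.** It takes at most 8.7 weeks out of the treatment segment. It also removes selection-related regression for the repeated measure, to the extent that its error is independent of the screening score. It leaves 13-19 weeks of natural change mixed with treatment.

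**The case against.** The strongest reply is that this is a small Stage 1B study whose stated purpose is only to "Explore the preliminary effects of the intervention on select outcomes". Section 7.2 is descriptive and introduces the outcomes as preliminary, and Section 5.4 concedes the missing comparator. The probable bias is well inside the sampling error. The two-month rule already limits drift, and its rationale suggests that the retake is meant to replace the first baseline. All of this stands and lowers the weight of the point. It does not remove it: a wide interval shows imprecision, but it does not show the reader a shift in one direction.

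Three stronger readings are tempting and are not supported.

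- A reader might infer that the plan credits COACH with the whole change. The text makes no such claim; it simply does not distinguish the two intervals.
- A reader might infer that weekly symptom surveys already allow the separation. In Table A the word weekly belongs to the questions that prepare therapy sessions. Weekly symptom assessments appear only in the summary of revisions, and Section 5.8D makes the outcome and mechanism surveys monthly. No collection before session 1 is stated.
- A reader might infer that all outcomes are biased towards benefit. The veteran severity rule in Section 5.9 is a CAPS-5 diagnosis, with no veteran PCL-5 or PHQ-9 cut-off stated. The functioning scales are not selection variables. Loved ones are excluded for a positive PCL-5 screen, so their scores would tend to regress towards worsening. Section 5.8C gives drift no direction, and its clinical examples are deteriorations.

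It is also fair to object that the split helps least where selection is most direct: Table A places the structured interview only at baseline and posttreatment, so the CAPS-5 cannot be divided.

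**Conclusion.** The point holds as a modest, correctable weakness in how symptom change is reported. The documents themselves show the double use of the baseline, its permitted age, and the silence of Section 7.2 on the interval before session 1. For veterans' symptom scores the selection effect would favour improvement by about 0.02 to 0.40 selected-sample SD. The whole range rests on the assumed pass rates, retest correlations and cut-like selection. It fits the CAPS-5 most directly and should be read as generous for the PCL-5 and PHQ-9. Drift over the wait cannot be sized or signed from the documents. The amendment is worth making because it costs little, not because the bias dominates the result.

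**What to change.** 1. Require the first symptom survey in the during-treatment series (Table A) to be completed before session 1 begins, and name its instrument. The assumption here is that it contains the PCL-5, the PHQ-9 or both.
2. In Section 7.2, for that self-report measure, report baseline to session 1 and session 1 to posttreatment beside the total change, with an effect size for the second segment.
3. State that a retaken baseline is the pretreatment value where there is one. Keep the first baseline and show the change between the two as a descriptive untreated interval; it may rest on very few couples.
4. Add to Section 5.4 that CAPS-5 and functioning changes still include the interval before session 1, that the CAPS-5 change also carries selection-related regression to the mean, and that natural change during treatment cannot be separated in a single arm.

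The cost is a sentence on survey timing, an extended change table and a few sentences of text. The symptom effect may look smaller, and the split covers only the repeated self-report measure. If the existing survey contains neither the PCL-5 nor the PHQ-9, one short extra administration is needed.

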7.3 Withdrawal of Subjects

Participants can withdraw from the study at any point in time and for any reason by contacting study personnel in person, by telephone, or by mail, and requesting to withdraw. We anticipate termination of participation if:

1. The participant becomes ineligible to participate.
2. The participant does not follow instructions from the researchers.
3. The study is unexpectedly suspended or canceled.

8.0 Reporting

We will follow the VA Central IRB Table of Reporting Requirements for all issues that must be reported (i.e. summary of adverse events, unexpected problems and any actions or changes with respect to the protocol).

Adverse events (AE) include any untoward medical occurrence in a patient or clinical investigation subject administered an intervention and which does not necessarily have a causal relationship with this treatment. We will collect the following safety information (adverse events) that occurred within 7 days leading up to the final assessment.

1. Suicide attempts
2. Hospitalizations for mental health
3. Episodes of severe IPV

Therapists will be instructed to notify study staff immediately when such events occur during treatment delivery. Staff will report directly to the PI regarding any events. Therapists will also meet regularly for case consultation, where the occurrence of any of these events will be further discussed and tracked. Questions regarding the occurrence of each of these three events will be included in posttreatment assessments. Data obtained from participants will be reviewed for safety concerns. In the case of problems, the staff will discuss this with the PI.

Of note, survey reports of IPV on posttreatment and follow-up surveys will be reported when respondents endorse items consistent with severe violence. This includes the following: (1) hit my partner with a fist or something hard, (2) kicked my partner, (3) slammed my partner against something, (4) beat my partner, (5) burned my partner on purpose, (6) tried to hurt my partner by choking or suffocating him/her, or (7) used a knife or gun on my partner. Examples of serious adverse effects, according to the FDA, include death, life- threatening adverse events, suicide attempts, and hospitalization. Consequently, endorsement of items 6 or 7 will be considered a SAE. Given the population, some incidents of severe IPV are expected. Reports of moderate to severe IPV on baseline surveys are part of our exclusionary criteria (see inclusions/exclusions). Thus, severe IPV in reported in baseline surveys will not be reported as adverse events.

The PI and Co-Is are all licensed clinical psychologists. Events will be immediately communicated to the study PI. The team will in turn will report any problems to the IRB. Once the PI learns of any SAEs, UAP, compliance issues, RCO, and/or protocol deviation, the team will report these events. If there are modifications or amendments to the study the study PI will also submit appropriate amendments and wait for approval prior to implementation.

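### Section 8.0 limits safety-event collection to 7 days before an undefined final assessment, leaving most post-treatment days without a stated query for suicide attempts or psychiatric admissions

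*Combined protocol and SAP*

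**What the plan says.** Section 8.0 names three safety events: suicide attempts, mental health hospitalizations and severe IPV. It then gives several rules for collecting them.

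- The general rule: "We will collect the following safety information (adverse events) that occurred within 7 days leading up to the final assessment".
- During treatment: "Therapists will be instructed to notify study staff immediately when such events occur during treatment delivery". At case consultation, "the occurrence of any of these events will be further discussed and tracked".
- After treatment: "Questions regarding the occurrence of each of these three events will be included in posttreatment assessments". No recall period is given for these questions.
- For violence only: "survey reports of IPV on posttreatment and follow-up surveys will be reported when respondents endorse items consistent with severe violence".
- In general: "Data obtained from participants will be reviewed for safety concerns", and "Once the PI learns of any SAEs, UAP, compliance issues, RCO, and/or protocol deviation, the team will report these events".

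The schedule does not settle which assessment is final. Section 5.4 describes a pre-post design. Section 6.1 has surveys at baseline, during treatment and within four weeks of the final COACH session. Section 5.6A (A.2 and Table A) adds a survey 3 months after the final session, which the revision history attributes to Amendment 14.

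**The concern.** The 7-day rule depends on a term that has two candidate meanings, and it does not fit the sentences around it. A therapist-reported admission in mid-treatment, or severe IPV endorsed on a survey with a longer recall, is reportable under one sentence and outside the window of another. They cannot all define one collection period.

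The asymmetry matters most. Section 8.0 itself gives suicide attempts and hospitalization as examples of serious events. Yet for follow-up surveys it names only IPV. Once sessions end, the therapist route ends too, and these two event types rest on questions whose only stated period is 7 days.

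No analysis in Section 7.2 uses these counts, so no estimate is at risk. The stake is the safety record. Section 8.0 commits the team to a summary of adverse events, and Section 5.1 says the study is to support an application for a randomized trial. With 12 veterans planned, one event is 1/12 = 8.3% of the sample. A low post-treatment count could reflect the collection rule rather than few events.

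**Working it through.** The plan states no coverage figure, so there is nothing to reproduce. The check counts days.

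**Inputs**

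- Look-back: 7 days (Section 8.0).
- Posttreatment survey: day t after the final session, t = 0 to 28 (Section 6.1, within four weeks). The event questions are assumed to be asked that day.
- 3-month survey: day H after the final session (Section 5.6A, A.2). H = 91 is assumed.
- Therapist route: taken to end at the final session, because Section 8.0 ties it to treatment delivery.

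**Formula.** Days without a stated query for attempts or admissions = H minus the days after the final session that fall inside at least one look-back window.

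| Reading | Formula | Days of 91 | Share |
|---|---|---|---|
| A. Final assessment is posttreatment; 7-day recall | 91 − min(t, 7) | 84–91 | 92.3–100% |
| B. Final assessment is the 3-month survey; only that window counts | 91 − 7 | 84 | 92.3% |
| C. 7-day recall at both | 91 − min(t, 7) − 7 | 77–84 | 84.6–92.3% |
| D. Posttreatment questions reach back to the final session or earlier; nothing at 3 months | 91 − t | 63–91 | 69.2–100% |
| E. As D, plus 7 days before the 3-month survey | 91 − t − 7 | 56–84 | 61.5–92.3% |

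The upper ends are at t = 0. The lower ends are at t = 28 for D and E, and from t = 7 onward for A and C. Taking H as 90 or 92 moves each bound by one day.

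The gap would be 0 if the 3-month survey asked about everything since the previous assessment and the posttreatment questions reached back to the final session. Section 8.0 does not say so. It names posttreatment and follow-up surveys separately, Table A gives them separate columns, and only IPV is tied to follow-up.

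**Other routes after the final session**

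- Survey screening (Section 5.6B, B.1) looks for expressed suicide or homicide risk and notifies the veteran's provider. It is not a question about past events.
- The posttreatment structured interview covers PTSD symptoms. The exit interviews cover acceptability, engagement and perceived impact (Sections 5.6A and 6.1).
- Staff calls in Tables 3 and 4 of Section 6.4 concern survey completion.
- Reporting by the team depends on the PI learning of an event.
- The administrative data listed in Section 6.1 include sessions attended but not admissions.

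Each could bring an event to light. None is a stated query about past attempts or admissions.

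**Couples who stop early.** Survey timing is anchored to the final COACH session. Those who miss it are sent the survey, but no date is given. Table 3 in Section 6.4 has a prenotice for dropout dyads without tying its Day 0 to a calendar point. Neither t nor H is known for them.

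**The case against.** The strongest reply is that the 7-day sentence is not the whole system. All three events are asked about in posttreatment assessments with no recall limit, and trained staff still meet or call participants at the posttreatment interview, the exit interviews and both survey rounds. The item wording sits in a materials document that is not available here, and Section 8.0 also defers to a VA Central IRB reporting table that is likewise unavailable. On this view the documents show an undefined term and a missing cross-reference, not lost events.

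Much of this stands, and it rules out several stronger readings:

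- A reader might infer that events during treatment are missed. They are not: therapists notify staff at once and track events, and loved ones are part of every session (Section 3.0).
- A reader might take 84 to 91 of 91 days as the settled figure. It holds only if the 7-day limit governs the posttreatment questions or applies only at 3 months.
- A reader might apply the 91-day count to couples who stop early. Their survey timing is not stated.
- A reader might turn days into a share of events missed. The documents give no event rates.

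What the reply does not remove is the contradiction inside Section 8.0, or the absence of any stated question on attempts or admissions at 3 months. If the materials document already uses a longer recall, Section 8.0 still has to be brought into line with it.

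**Conclusion.** The concern holds as a defect in the stated collection rule. The final assessment is undefined, the 7-day limit conflicts with other sentences in Section 8.0, and for couples who attend the final session 56 to 91 of about 91 days (62 to 100%) have no stated query for suicide attempts or mental health hospitalizations.

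The figure rests on 3 months being 91 days, on posttreatment questions asked 0 to 28 days after the final session, and on the five readings tabulated. It is a share of days, and it describes what the protocol states rather than what the survey items may contain. It should be fixed because every reading computed leaves more than half the period uncovered for the two event types. Confidence is medium, because the item wording could not be seen.

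**What to change.** In Section 8.0, replace the 7-day clause with a period running from the first treatment session through the 3-month follow-up survey. This fits the section's own definition of an adverse event, which refers to a "subject administered an intervention". Then state that:

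- suicide attempts and mental health hospitalizations are asked about in the existing posttreatment assessment, with recall since treatment began;
- both are asked about again in the existing 3-month survey, with recall since the last completed survey, or since treatment began if the posttreatment survey was missed;
- couples who stop early are asked the same questions;
- the existing IPV items are kept, and the therapist and IPV sentences are made consistent with this period.

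The cost is one sentence in Section 8.0, recall wording on two existing assessments, and two added items at 3 months if they are not already there. The downsides are slightly more survey burden, less exact recall over a longer period, and possibly a few more events to report. Extracting admissions from records and reporting counts by source would be optional additions. Extraction would need a check that the consent and HIPAA wording covers it.

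### Active safety collection in Section 8.0 covers three event types only; death, other life-threatening events and non-psychiatric hospitalization, cited as serious in the same section, are picked up only passively

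*Combined protocol and SAP*

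**What the plan says.** Section 8.0 (Reporting) opens with a wide definition: "Adverse events (AE) include any untoward medical occurrence in a patient" and so on, whether or not treatment caused it. It then sets out what will be gathered: "We will collect the following safety information (adverse events) that occurred within 7 days leading up to the final assessment". Three items follow: "Suicide attempts", "Hospitalizations for mental health" and "Episodes of severe IPV".

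Two active routes feed that list.
- Therapists: "Therapists will be instructed to notify study staff immediately when such events occur during treatment delivery".
- Participants: "Questions regarding the occurrence of each of these three events will be included in posttreatment assessments".

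Further down, the section turns to seriousness: "Examples of serious adverse effects, according to the FDA, include death", followed by life-threatening events, suicide attempts and hospitalization. The last of these is not restricted to psychiatric admissions. The only explicit classification rule drawn from those examples is that two of the seven severe-violence survey items (choking or suffocating; knife or gun) count as serious adverse events (SAEs).

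Section 8.0 also says that the team will follow the VA Central IRB reporting table, review participant data for safety concerns, and report any SAE once the PI learns of it. The Communication Plan (Section 10.0) repeats the commitment to inform the IRB of SAEs.

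**The concern.** The list that drives data collection is narrower than both the adverse event definition above it and the serious-event examples below it. A medical or surgical admission, a death, or a life-threatening event that is neither a suicide attempt nor severe IPV has no question attached to it and no instruction to therapists to notify staff. The reporting commitments apply once such an event is known, but Section 8.0 describes no step that would make it known.

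At stake is the completeness of the safety record from a first trial of a new couple-based exposure therapy that the sponsor intends to take into a randomized trial (Section 5.1). If collection follows the section as written, serious events can go unrecorded, and a reader could not tell an absence of events from an absence of questions.

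**Working it through.** The plan states no safety count or rate, so there is no figure to reproduce. The check is to set the section's own serious-event examples against its two active routes.

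| Serious-event example (Section 8.0) | Posttreatment question | Therapist notification |
|---|---|---|
| Death | none | none |
| Life-threatening event | only if it is also one of the three listed events | same |
| Suicide attempt | yes | yes |
| Hospitalization | mental health only | mental health only |

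One of four is fully covered, two of four partly, and one of four not at all.

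**Does another source fill the gap?**
- *Administrative data.* Sections 5.6A (A.2) and 6.1 list sessions attended, numbers screened, numbers declining and therapist homework ratings. Hospitalizations are not extracted.
- *Loved ones.* They make up half of each dyad and need not be VA patients; Section 5.6B provides for participants who are not Veterans. No records route is described for them.
- *Dropouts.* Therapist notification applies during treatment delivery. Those who miss the final session are sent the survey (Sections 5.6A and 6.1), and the planned safety questions concern the three listed events.
- *3-month follow-up.* Section 8.0 places the three questions in the posttreatment assessments and mentions follow-up surveys only for severe IPV.
- *Reporting commitments.* Sections 8.0 and 10.0 cover SAEs without restriction to the list, but they take effect after the PI is aware of one. The contents of the IRB table are not in the document, so I give it no weight either way.

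**The look-back window.** Adding a question would help little if it inherited the 7-day window. Section 5.2A gives weekly sessions, typically 13 to 15 of them. Counting one week per session:
- 13 × 7 = 91 days, and 7 / 91 = 7.7%
- 15 × 7 = 105 days, and 7 / 105 = 6.7%

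A 7-day recall therefore spans about 7% to 8% of a typical course. Section 6.1 also allows the posttreatment survey up to four weeks after the final session, so the window may contain no treatment time at all.

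**The case against.** The strongest reply is that this is a deliberate, proportionate list. The study is a small open pilot, described in Section 5.6A as minimal risk with no physical risks expected. The three items are the foreseeable harms of trauma-focused couple work. Any other SAE that becomes known is still reported. Couples are seen weekly for 90 minutes, so a death or an admission that interrupts sessions would probably surface during treatment. An injury caused by a partner is not wholly invisible either: severe IPV is asked about directly on posttreatment and follow-up surveys, and both partners answer. What is left is mainly admissions unrelated to IPV or a suicide attempt.

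Much of that stands, and it limits the point. It does not remove it. Weekly contact ends with treatment and never applied fully to dropouts. The section gives no reason for restricting hospitalization to mental health, and it does not say that the list is meant to be narrower than its own examples.

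A reader might go further and infer that SAE counts cannot agree with the protocol's SAE definition. The documents do not support that. The protocol offers FDA examples, not a formal definition. It mentions hospitalization without qualification but never states that every admission is an SAE. Section 7.2 plans no SAE count or rate. Unlisted events can still enter through the PI.

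**Conclusion.** The mismatch within Section 8.0 is real and should be reconciled. Active collection is limited to three event types. Other serious events cited in the same section are captured only if the PI comes to know of them, so their ascertainment is passive and may be incomplete, especially for loved ones, dropouts and the period up to the 3-month survey.

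The consequence is possible under-recording of an unknown number of events. The documents give no event rate from which to estimate it, and no planned efficacy, acceptability or feasibility analysis is affected. This is a low-cost correction worth making, not a critical flaw.

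The conclusion assumes that the full survey battery, which sits in a separate Materials document not supplied here, does not already ask about hospitalization for any cause. If it does, the gap narrows to Section 8.0's wording, its notification list and its look-back window.

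**What to change.** In Section 8.0:
1. Change item 2 to hospitalization for any cause, with the reason recorded, so that mental-health admissions can still be summarized separately.
2. Add death and other life-threatening events to the events that therapists and staff must notify. Death belongs on this route because participants cannot report their own.
3. Ask the matching hospitalization question of Veterans and loved ones at posttreatment and in the 3-month survey, covering the whole period since treatment start and not only the 7 days before the final assessment.

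The cost is one or two survey questions, a short wording change and an amendment. The downside is that some hospitalizations unrelated to the study will be recorded and will need the reason noted.

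If the sponsor prefers the short list, the minimum is a sentence saying that it is deliberately targeted and that other serious events are captured passively. That would remove the inconsistency in the text but would not improve ascertainment.
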